Patients for the feasibility study will be recruited from the gastroenterology outpatient clinic at Bispebjerg Hospital, Copenhagen. Patients will be identified and invited by nurses and physicians at the outpatient clinic, who will describe the project and provide patients with written information about the project. If identified patients are willing and eligible to participate according to in – and exclusion criteria, the outpatient clinic staff will pass on the patients' contact details to intervention leader, TT, or a project nurse, employed at the gastroenterology department. Either TT or the project nurse will then contact the patients by telephone and invite them and a relative (if wished for) to an information meeting at the gastroenterology department. Here, the patients will receive oral information on the project by TT in a private room. This information will include the purpose, methods, time frame and possible risks of participating with sufficient time for the patients to understand and ask questions. Furthermore, the patients will be informed about the possibility of declining any new information on their health status that may emerge during the study, and additionally, the possibility to withdraw their consent at any time without it affecting their current treatment in the clinic. If patients decide to participate in the study during the information meeting, they will sign a written consent. However, patients will also be offered 48 hours

to reflect and decide on participation or not. Either TT or the project nurse will then obtain their signed consent at a later stage in the clinic.

Randomization and blinding

Study participants will be randomly assigned (1:1) to either an intervention group (n=15) or a control group (n=15). The randomization will be conducted through the REDCap (Research Electronic Data Capture) platform (see description under 'data management'). The allocation sequence will be concealed from the project leaders. It will not be possible to blind participants and project staff delivering the intervention to allocation status, whereas all outcome data will be collected by blinded outcome assessors.

Intervention

The intervention is an individually tailored, behavioural intervention addressing the individual patient's knowledge, motivation, resources and opportunities for increasing daily physical activity in the individual's everyday life.

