The 20-week intervention will consist of a basic part for all participants, which will include

- 1) A group session with education about IBD in general and about physical activity and exercise in relation to IBD (definitions, evidence and recommendations). Following this session, the participants will also be offered access to a video with general information about IBD, physical activity and exercise
- 2) Four individual motivational counselling sessions (two physical and two telephone sessions) with a project nurse. The counselling sessions will involve identifying the individual's motivation and opportunities for increasing physical activity, behavioral goal setting and action planning.

[figure not shown]
An optional intervention part will then follow, where the individual participant will have the possibility of choosing between (or all of)

- 1) A one-hour individual session with a physiotherapist from Bispebjerg/Frederiksberg Hospitals, which will involve guidance in physical activity and exercise tailored to the individual participant. This could be the case if a participant experiences specific symptoms or limitations when engaging in physical activity and/or exercise and needs individual guidance related to this.
- 2) Being teamed up with 1-2 'exercise buddies' (other participants from the overall intervention group). During the intervention development phase stakeholders (patients with IBD) argued for the possibility of being physically active/exercising with others in small groups to increase motivation

and sustain physical activity behaviour, which is why we would like to offer this as an optional element of the intervention.

- 3) Access to 5-10 short 2-3 minutes videos/'reels' of a physiotherapist explaining and demonstrating beneficial physical exercises. With these videos we aim to provide participants with new inspiration and practical suggestions to increase their physical activity and exercise.

Figure 2 illustrates the intervention content and flow, including an initial group session, four nurse-led motivational counselling sessions and an optional part with physiotherapist-led sessions, the possibility of teaming up with a 'exercise-buddy' and short inspirational videos.

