The main setting of the intervention will be the participants' everyday lives (family, work/school, leisure-time activities). However, the Gastroenterology Department, Bispebjerg Hospital, and potentially, local municipal health centres and sports clubs will be the actual physical places for the specific intervention elements (e.g. education, counselling sessions, physiotherapist-led sessions, exercising in small communities ('exercise buddies')). As the intervention focuses on and takes place in an 'everyday life'

setting, we expect the intervention to be realistic and implementable in the gastroenterology clinic and/or the municipal health centres subsequently.

Control group

Participants randomized to the control group will be encouraged to maintain their usual lifestyle and activities. They will be expected to undergo the same baseline – and outcome assessment as the participants in the intervention group.

Outcome measures

The primary focus of the study is to investigate study feasibility and acceptability, including investigating facilitators/barriers for recruitment, acceptance of group allocation, study retention, the quality of delivery methods, intervention fidelity (project staff's fidelity to intervention manual), participants' perception of the developed intervention and the adherence to outcome assessments. Assessment of intervention fidelity and acceptability will include qualitative methods such as observations of the intervention elements and interviews with participants and project staff. The specific outcome assessments in the feasibility study will include a range of both objectively measured outcomes and self-administered questionnaires.

Objectively measured physical activity

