The SENS motion[®] (SENS Innovation ApS) is a waterproof activity sensor (45 × 23 × 5mm, 6 g), which the participants will wear laterally on the right thigh (20). The sensor is placed in a small patch specially designed for the SENS sensor and is attached on the skin with adhesive tape. The sensor is a triaxial accelerometer, which samples at 12 Hz and registers the orientation and acceleration of the thigh. Based on this orientation and acceleration, the sensor captures seven-day, 24-hour physical activity patterns, including number of steps and the amount of daily time lying down, sitting, standing, and being active with light, moderate and high intensity, as well as specific activities such as bicycling or walking stairs (28). SENS is used primarily as a single sensor system, but a dual-sensor algorithm has been developed to enable distinction between different sedentary positions, including sitting with inclined and upright backrest. Therefore, for the present study, we expect that two sensors will be used (one placed on the thigh and one on upper back). Patients will simultaneously be asked to fill in a diary reporting what time they get up in the morning, go to work, finish work and go to sleep for the seven-day measurement period.

Self-reported physical activity and sitting time

Self-reported physical activity (light, moderate, vigorous) and sitting time at work and during leisure time will be measured by the Physical Activity Scale 2.1 (PAS 2.1) (21), a modified version of the original PAS

questionnaire, which has previously been validated against accelerometer, physical activity logs and maximum oxygen uptake (22,23). Respondents will be asked to specify number of hours and minutes in an average 24-hour day spent sitting at work and during leisure time. In addition, participants will report number of weekly hours and minutes spent in light, moderate or vigorous intensity activities.

The participants will be asked to respond to PAS 2.1 at baseline and again at the 20-week follow-up assessment. In addition, the project nurses will conduct a telephone-based mini-survey four times with each participant during the intervention period in order to monitor changes in physical activity behaviour in-between the two outcome assessment times. The survey will consist of three questions about the participant's weekly time spent on moderate to vigorous physical activity, light-intensity physical activity and sedentary behaviours.

Exercise self-efficacy

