Outcome assessment will be conducted at study inclusion/baseline and repeated at end of the intervention period (20 weeks (five months) from baseline) for each of the 30 participants. Participants will complete self-administered questionnaires regarding demographics, lifestyle, physical activity, disease-specific quality of life, pain, fatigue and intrusiveness of IBD. Anthropometric measures, blood pressure, fecal calprotectin test and a single blood sample will be obtained at the same time points by a project nurse. Calprotectin test and blood samples will be analyzed at Department of Clinical Biochemistry, Bispebjerg Hospital, for inflammation biomarkers and lipid status. In addition, the same project nurse will attach the SENS motion activity sensor on the participants' thigh and instruct participants how to wear the monitors 24 hours per day for seven continuous days. The activity sensors connect wirelessly to a smartphone application, and the recorded data are transmitted to the application every 10 minutes, when the smartphone is within network reach or stored on the sensor for later transmission. The raw triaxial accelerometer data are transferred automatically to a secure web server (Capital Region, Denmark) via the smartphone. During each assessment the participants will fill in a daily report of their resting and sleeping time in order to isolate their sitting time from sleeping time. After the seven-day assessment period the participants will remove the sensor and keep it until the next appointment at Bispebjerg Hospital, where they will return it to the project nurse.

Data collection from feasibility and acceptability

Regarding data on feasibility and acceptability, the intervention leader (TT) will document all components of the recruitment and screening procedure. This will include documentation of the number of invited and screened patients and reasons for exclusion or declining study participation. Acceptability and fidelity to the intervention elements and outcome assessments will be evaluated through interviews with project staff delivering the intervention and with five study participants. Furthermore, this will be monitored using a log sheet in which information on intervention progress and retention will be registered.

Data management

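### Is it a flaw that the protocol does not say whether participants learn their arm before or after the seven-day baseline sensor recording?

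*Combined protocol and SAP*

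**What the plan says.** All places are in the combined protocol and SAP.

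- **Randomization and blinding.** Allocation is 1:1, 15 per arm, through REDCap, with the sequence concealed from the project leaders. On blinding: "It will not be possible to blind participants and project staff delivering the intervention to allocation status". No time is given for the draw or for telling participants the result.
- **Control group.** The text reads: "Participants randomized to the control group will be encouraged to maintain their usual lifestyle and activities. They will be expected to undergo the same baseline"; the sentence goes on to include the outcome assessment, with the intervention arm as comparator.
- **Data collection from outcome assessments.** "Outcome assessment will be conducted at study inclusion/baseline and repeated at end of the intervention period", the latter set at 20 weeks from baseline. The nurse attaches the sensor at the assessment and it is worn for seven days. Then: "After the seven-day assessment period the participants will remove the sensor and keep it until the next appointment at Bispebjerg Hospital".
- **Intervention.** The programme lasts 20 weeks. It includes one group session and "Four individual motivational counselling sessions (two physical and two telephone sessions) with a project nurse".
- **(Statistical) analyses.** The primary analyses concern feasibility. Changes from baseline are summarised by mean and SD, within and between arms. The SDs of sensor-measured activity will be used to size the later trial.

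**The concern.** Most baseline measures are taken at one visit, so their order relative to disclosure is easily kept. Sensor-measured activity is different: it builds up over the week after the visit, and it is the behaviour that the intervention aims to change. If participants already know their arm during that week, the recording is partly a post-allocation measure. Intervention participants might start moving more, and disappointed controls might wear the sensor less.

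Three things would then be at stake: the descriptive differences in change, the completeness of baseline sensor data by arm, and the SDs passed on to the later trial. Acceptance is itself under study, since the Outcome measures section lists "acceptance of group allocation, study retention" among its targets. A control who reacts badly during wear might show up as incomplete baseline data, and one who reacts afterwards as a retention loss. The literal wording of the Control group section, in which people already randomised still have baseline ahead of them, makes the gap look like more than an omission.

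**Working it through.** The plan gives no figure to reproduce, so the check consists of the text, the calendar and the possible effect.

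**1. Does any text fix the order?**

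| Section | What it gives | What it says about order |
|---|---|---|
| Randomization and blinding | ratio, platform, concealment, no participant blinding | nothing |
| Control group | same assessments in both arms | none stated; allocation first only if read literally |
| Data collection from outcome assessments | baseline at inclusion, seven days of wear, sensor returned later | randomisation not mentioned; baseline first is the natural reading |
| (Statistical) analyses | change from baseline in each arm | nothing |

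The Control group sentence uses the arm label to say who is meant, and its subject is equal assessment. The two middle rows are therefore compatible. The text leaves a detail open; it does not contradict itself.

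**2. Does the calendar settle it?** Inputs: a 20-week intervention (Intervention section), follow-up at 20 weeks from baseline and seven days of wear (both in the data collection section).

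- 20 × 7 = 140 days from baseline to follow-up.
- If that count starts at the baseline visit and disclosure waits for the end of wear: 140 − 7 = 133 days, or 19 weeks, of intervention.
- If baseline means the end of wear, the full 140 days remain.

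The calendar fits either order, with a difference of one week in 20. It does not show that disclosure precedes wear.

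**3. What could early disclosure do to the results?** Write the between-group difference in change as D = (F_I − B_I) − (F_C − B_C), where F is the follow-up mean, B the baseline mean, I intervention and C control.

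- If knowing the arm shifts B_I by b, D becomes D − b. A shift in B_C moves D by the same size in the other direction.
- If k of the seven days fall after disclosure, and each such day is shifted by d (an assumption, for illustration), then b = (k/7) × d. Here k can be anything from 0 to 7, and k = 0 when disclosure follows wear.
- The documents give no value or range for d, so b cannot be sized.
- A shift that is equal for everyone in an arm leaves the SD within that arm unchanged. The SDs for the later trial would be disturbed only if people reacted unevenly, or if the arms were pooled without regard to group.

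**4. Which outputs depend on the order?** The counts of screened and eligible patients and of intervention elements received do not. The change summaries, the baseline sensor completeness by arm and the sensor SDs might. No hypothesis test is planned on the change scores.

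**The case for a change.** The strongest case for a change is that a study meant to prepare a randomised trial ought to specify and rehearse this sequence, and that a few sentences would do it. The documents also name no occasion on which controls are told their arm. The intervention arm has three named in-person contacts after baseline (one group session plus two physical counselling sessions, 1 + 2 = 3), while controls have none before week 20 apart from the unspecified appointment for returning the sensor. The telephone surveys do not help, because "the project nurses will conduct a telephone-based mini-survey four times with each participant during the intervention period" places them after allocation.

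Some of this stands. The order is not written down, and it would be good to have it written down. The rest carries less weight:

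- Disclosure needs no visit; a telephone call is enough. The documents name no disclosure contact for either arm, so counting contacts says nothing about order.
- The sensor-return instruction belongs to a description that covers both assessments, and reads as general logistics.
- With 15 per arm, one control who stopped wear would be 1/15 = 6.7% of the arm. That is a hypothetical person and not an estimated effect. The plan sets no minimum wear time, and recordings are transmitted or stored as they accrue, so early removal leaves partial data.
- Putting wear first has a price if follow-up stays at 20 weeks from the visit: the intervention loses the week computed above.

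The Data management section adds some reassurance. Randomisation is done in REDCap, where tasks in the record form are logged. Disclosure cannot precede the draw, so a logged draw after the end of wear would settle the question for that participant. A draw before then would leave it open.

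**Conclusion.** No change to the plan is needed. The timing of randomisation and disclosure relative to the baseline recording is a missing detail. No stated rule puts disclosure before or during wear. Baseline at inclusion agrees with the usual order (consent, baseline visit, completed wear, then disclosure and first session), which investigators would be expected to follow without being told. An amendment would mainly record that practice.

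The possible damage is confined to descriptive change scores, baseline sensor completeness by arm and sensor SDs in a 30-person feasibility study. It is zero if disclosure follows wear, and otherwise equals a shift that the documents do not allow to be estimated. The remaining looseness in when the 20 weeks start amounts to 7 of 140 days.

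This rests on two assumptions: that staff do follow the usual order, and that the intervention figure, which is not shown in the available text, sets no contrary timing. Its description covers only intervention content and flow.

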A venous blood sample will be drawn (not fasting). Total cholesterol, high-density lipoprotein cholesterol (HDL), and triglycerides will be measured. Low-density lipoprotein cholesterol (LDL) and very low-density lipoprotein cholesterol (VLDL) will be calculated by the formulae: $VLDL = \text{Triglyceride} \times 0.45$ and $LDL = \text{Total cholesterol} - HDL + VLDL$. In addition, C-reactive protein (CRP), albumin and glycosylated hemoglobin, type A1c (HbA1c) will be measured.

Blood pressure

Blood pressure will be measured, after 5 to 10 minutes of rest, 3 times at the right upper arm (average of the 3 measurements) with the participant in a sitting/lying position.

Anthropometric measures

Anthropometric measures such as height, weight and waist- and hip circumference will likewise be included in the assessments. Height is measured without shoes to the nearest centimeter; weight is measured in light clothing without shoes to the nearest 0.1 kg; waist circumference is measured midway between the lower rib margin and the iliac crest to the nearest 0.5 centimeter, without any pressure to the skin and with an unstretched tape measure; hip circumference is measured at the point yielding the maximum circumference over the buttocks to the nearest 0.5 centimeter. The tape should be held in a horizontal plane touching the skin but not indenting the soft tissue. Body mass index (BMI, kg/m²) and waist-hip ratio will be calculated.

Demographic and clinical information

In addition, information regarding demographics (e.g. sex, age, education, civil status, employment) and lifestyle (smoking and alcohol consumption) will be obtained by self-reports while data on disease location

and duration, disease severity, surgery, medical treatment and active co-morbidities in form of disease in joints, skin, pancreas, thyroid, lungs or liver and prescriptions (FMK) will be collected from Epic (Sundhedsplatformen). The researchers' direct access to the electronic patient records and retrieval of these data will be depended on signed informed consent from the relevant participant. Information on diagnosis and medical treatment is necessary for identification and screening of the participants (see in- and exclusion criteria) before an eventual signing of informed consent.

Data collection from outcome assessments

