All data in the feasibility study will be collected and managed using an electronic case record form (eCRF), which is based on REDCap (Research Electronic Data Capture) (29), hosted at the Capital Region, Denmark. REDCap is a secure, web-based application designed to support data capture for research studies, providing 1) an intuitive interface for validated data entry, 2) audit trails for tracking data manipulation and export procedures, 3) automated export procedures for seamless data downloads to common statistical packages and 4) procedures for importing data from external sources. Center for Clinical Research and Prevention, Bispebjerg and Frederiksberg Hospitals, will act as the project owner in REDCap. All access to the server and other server maintenances will be logged. Study setup and hosting will be performed by Bispebjerg Hospital. Only authorized access to the eCRF will be possible using encrypted username and password. Roles in the system are given according to functions (project leader, study nurse etc.). All tasks performed in the eCRF are logged in an audit trail. The project leaders and authorized project staff can add data to the eCRF and will keep the eCRF current to reflect subject status during the study period. The project personnel will make a separate confidential record of personalized details (name and initials) and enrollment log on the individual participant, which is kept separately from the eCRF. Once the eCRF for a participant is completed, the authorized staff will approve the data using an electronic signature and thereby confirm the accuracy of the data recorded.

(Statistical) analyses

The primary analyses will be of feasibility outcomes. We will report the numbers of screened and eligible participants seen over the recruitment period, and the rates of retention and adherence, that is proportion of participants completing outcome assessments and receiving intervention elements (both basic and optional elements). In addition, we will ascertain data completeness of the instruments and any potential bias in the completion of follow-up data to inform the choice of instruments in a future randomized controlled trial. Also, we will use the results (standard deviations) from the objectively measured physical activity levels to determine the appropriate sample size for the later randomized controlled trial.

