Descriptive statistics in the feasibility study will give insight into participants' characteristics as well as distributions and indications of change in the outcome measures. The descriptive statistics will summarize categorical data (frequencies (%)) and continuous data (medians, means (M) and standard deviations (SD)). Changes in outcome measures from baseline to end of intervention will be reported as within-group differences (M and SD) in the intervention and the control group separately and between-group differences in change will be summarized (M, SD). All analyses will be conducted using SAS software (v. 9.3; SAS Institute Inc., Cary, NC, USA).

Risks and adverse events

The SENS motion activity sensor is sealed and placed in a small patch to avoid direct contact with the skin. The participants will be encouraged to change the location of the unit or contact intervention leader (TT) if the patch comes off or if they experience skin redness or itching. In our previous studies using activity monitors on patients with rheumatoid arthritis, few cases of redness and itching were reported as the only adverse events from using the monitors along with the inconvenience of having the unit attached to thigh and/or shoulder (17). Adverse effects such as muscle soreness, joint pain, muscle cramps and increased need to rest may be expected as participants are encouraged to be more physically active. Routine stool and blood samples are included in the study. The blood samples are taken by experienced staff and carried out in a quiet shielded room. A foreseeable risk involves the possible discomfort and small hematoma following the sampling of blood from the antecubital vein.

Ethical considerations

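### The LDL formula as printed adds VLDL instead of subtracting it, so each LDL value is too high by 0.9 × triglycerides and each LDL change is off by 0.9 × the triglyceride change

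*Combined protocol and SAP*

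**What the plan says.** The section on serum lipids, CRP and glycosylated hemoglobin (under Outcome measures) states which lipids are assayed: "Total cholesterol, high-density lipoprotein cholesterol (HDL), and triglycerides will be measured". The other two are derived: "Low-density lipoprotein cholesterol (LDL) and very low-density lipoprotein cholesterol (VLDL) will be calculated by the formulae". VLDL is triglycerides times 0.45, and LDL is "Total cholesterol} - HDL + VLDL". There are no brackets around the last two terms, no unit is given for the 0.45 factor, and no other section restates or corrects the formula.

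Under Data collection from outcome assessments, samples are taken at baseline and at 20 weeks and go to the hospital's clinical biochemistry department "for inflammation biomarkers and lipid status". That section does not say who calculates LDL.

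Under (Statistical) analyses, "The primary analyses will be of feasibility outcomes". Changes in the outcome measures are to be reported within each group, and "between-group differences in change will be summarized (M, SD".

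**The concern.** The formula is meant to obtain LDL by taking the other cholesterol fractions away from the total. It takes HDL away but adds VLDL back. LDL then contains VLDL twice over, compared with a version that subtracts it.

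This is not a constant offset that would cancel from change scores. It scales with each participant's triglycerides, so it carries into the baseline and 20-week levels and, wherever triglycerides change, into the mean changes. The between-group difference is affected wherever the triglyceride change differs between groups. If triglycerides fell more in the intervention group, the printed formula would tilt the LDL comparison in that group's favour.

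The protocol cites effects on cardiometabolic biomarkers in the earlier rheumatoid arthritis trial as part of its rationale, and it plans a full randomised trial next. An uncorrected formula could be copied into that trial.

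**Working it through.** **Inputs.** From the protocol: VLDL = 0.45 × TG, and LDL as printed = TC − HDL + VLDL (TC = total cholesterol, TG = triglycerides). Not printed in the protocol: the identity TC = HDL + LDL + VLDL, which is what makes subtraction right. The protocol contains no lipid values, so all values in mmol/L below are assumptions. There is no stated LDL figure to reproduce.

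**Coherence of the printed formula.**

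HDL + LDL + VLDL = HDL + (TC − HDL + VLDL) + VLDL = TC + 2 × VLDL = TC + 0.9 × TG.

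The parts exceed the whole for any positive TG. LDL alone exceeds total cholesterol whenever 0.45 × TG > HDL. With assumed TC 5.0, HDL 1.4 and TG 4.0, printed LDL = 5.0 − 1.4 + 1.8 = 5.4.

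**Error in level.**

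(TC − HDL + 0.45 TG) − (TC − HDL − 0.45 TG) = 0.9 × TG, whatever TC and HDL are.

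With assumed TC 5.0 and HDL 1.4 mmol/L:

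| TG | LDL as printed | LDL with VLDL subtracted | Error |
|---|---|---|---|
| 0.5 | 3.825 | 3.375 | +0.45 |
| 1.0 | 4.050 | 3.150 | +0.90 |
| 1.5 | 4.275 | 2.925 | +1.35 |
| 2.0 | 4.500 | 2.700 | +1.80 |
| 3.0 | 4.950 | 2.250 | +2.70 |

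**Error in change.** Writing Δ for 20 weeks minus baseline:

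Printed: Δ(TC − HDL) + 0.45 ΔTG. Subtracted: Δ(TC − HDL) − 0.45 ΔTG. Difference: 0.9 × ΔTG.

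For assumed triglyceride changes of 0.1 to 0.5 mmol/L, the error is 0.09 to 0.45 mmol/L, in the same direction as the triglyceride change. For an assumed fall of 0.3 mmol/L with HDL fixed:

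| Change in TC | LDL change as printed | LDL change with VLDL subtracted | Error |
|---|---|---|---|
| 0 | −0.135 | +0.135 | −0.27 |
| −0.135 | −0.270 | 0 | −0.27 |
| −0.30 | −0.435 | −0.165 | −0.27 |

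In the first row the sign of the change is reversed. An exact mirror image of this kind occurs whenever Δ(TC − HDL) = 0.

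**Between-group difference.** It is off by 0.9 × the between-group difference in ΔTG.

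**SD.** Var(printed) − Var(subtracted) = 4 × 0.45 × Cov(TC − HDL, TG) = 1.8 × Cov(TC − HDL, TG). The SD is therefore also wrong unless that covariance is zero. The same holds for changes, using the covariance of the changes.

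**The case against.** The strongest reply is that this is a slip of notation. One lost pair of brackets around HDL + VLDL would produce exactly this line, whether it was lost in typing or in converting the document. The hospital laboratory may well report LDL by its own method, so no value need ever be calculated this way. The subtracted version is itself only an estimate: it uses a fixed factor in a non-fasting sample, so 0.9 × triglycerides is not the error against a measured LDL. The sizes in mmol/L rest on assumed lipid values. The consequences for change summaries are conditional: the mean change is affected only if mean triglycerides change, the between-group difference only if that change differs between groups, and the SD only if the covariance is not zero. Finally, LDL is one of many descriptive outcomes among 30 participants, and the SDs named for the later sample size are those of objectively measured physical activity.

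Most of this stands as a limit on importance, and the conditional wording is right. None of it makes the printed line correct. Nothing in the document shows that brackets were lost, and the line is the only stated rule for deriving LDL. An analyst who follows it would code the wrong sign. If it is a slip, that is a reason to correct it.

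**Conclusion.** The concern holds. As printed, the formula is incoherent: it overstates each LDL value by 0.9 × triglycerides and misstates each LDL change by 0.9 × the triglyceride change, relative to the same formula with VLDL subtracted. Both multipliers are exact and follow from the printed 0.45 in any unit. The sizes in mmol/L depend on the assumed triglyceride values.

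The conclusion rests on two things: total cholesterol being the sum of its HDL, LDL and VLDL parts, and the formula being applied as written. The feasibility analyses and the planned sample-size input are untouched. Because all three component lipids are measured, any wrong LDL value can be recalculated without new data. It should be fixed before LDL is derived, but it does not threaten the study's main conclusions.

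**What to change.** - Print LDL = total cholesterol − (HDL + VLDL) in the serum lipids section.
- State the unit in which VLDL = 0.45 × triglycerides applies.
- State whether the laboratory or the study team derives LDL, and confirm that the laboratory and the analysis code use the corrected formula.
- Add one check per record that HDL + LDL + VLDL equals total cholesterol.

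The cost is one sign or one pair of brackets, a unit, a sentence on who calculates LDL, and one consistency check. It needs no new data item and adds no burden for participants or the clinic.
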